4.9.2 Clinical Laboratory Evaluations

The following summary will be provided for hematology, coagulation, chemistry, and lipid profile parameter for the OLE safety analysis set using the OLE data.

- Observed values and changes from the baseline by visit
- Worst toxicity grade
- \geq grade 3 toxicity post-baseline
- Shift from the baseline relative to the normal range
- Shift from baseline to worst toxicity grade

In addition, the number and percentage of participants with the following liver-related abnormalities will be summarized if meet the following criteria at any post-baseline visit.

- AST or ALT: (a) $\ge 3 \times ULN$; (b) $\ge 5 \times ULN$; (c) $\ge 8 \times ULN$
- Total bilirubin: $\geq 2 \times ULN$
- ALT or AST \geq 3 x ULN and total Bilirubin \geq 2 × ULN
- ALT or $AST \ge 5 \times ULN$ for more than 2 weeks

The following summary will be provided for urinalysis.

- Observed values and changes from the baseline
- Shift from the baseline relative to the normal range

Observed values and changes from baseline will be summarized descriptively for highsensitivity C-reactive protein (hs-CRP) and immunoglobulins parameters.

Listings will be provided for all clinical laboratory evaluations collected in this OLE study.

4.9.3 Vital Signs

The observed values, along with the changes from baseline, will be summarized for systolic blood pressure, diastolic blood pressure, body temperature, heart rate, and respiratory rate using the OLE safety analysis set based on OLE data. In addition, a summary of participants with clinically significant vital signs values (meeting any of following criteria) will also be provided.

- Systolic blood pressure: < 90 mmHg, > 160 mmHg
- Diastolic blood pressure: < 60 mmHg, > 100 mmHg
- Heart rate: < 50 beats/min, > 100 beats/min

- Respiratory rate: < 12 breaths/min, > 23 breaths/min
- Temperature: < 36°C, >38°C

4.9.4 Concomitant Medications

Medications collected during the trial will be coded using the current version of the World Health Organization Drug dictionary (WHO-DD). Number (%) of participants who received medications in this OLE study will be summarized by WHO-DD Anatomical Therapeutic Chemical (ATC) category and PT for the OLE safety analysis set. At each level of summarization, a participant is counted once if the participant reported one or more medications at that level.

The number and percentage of participants who receive rescue medications will be summarized. Rescue medications are:

- Any new permitted treatment to improve SLE disease activity, or
- An increase from Day 1 dose in this study in therapies, such as antimalarials, methotrexate, mycophenolate mofetil/mycophenolic acid, corticosteroid, or azathioprine.

The detailed rescue medications will be identified and finalized by medical monitor before database lock. The missing start/stop date will be imputed as appropriate, and the details of the imputation will be included in the SPP.

4.9.5 Electrocardiogram Results

The observed values, along with the changes from baseline, will be summarized for ventricular heart rate, PR interval, QRS duration, QT interval, and the corrected QT interval (QTc) using the OLE safety analysis set based on OLE data. The number (%) of participants meeting the following criteria will be summarized:

- QTc > 450 msec
- QTc > 480 msec
- QTc > 500 msec
- QTc increases from baseline > 30 msec
- QTc increases from baseline > 60 msec

Corrected QT (QTc) intervals will be derived using Fridericia's correction (QTcF) and Bazett's correction (QTcB). In addition, the overall clinical evaluation of electrocardiogram results (normal, abnormal, not clinically significant abnormal, clinically significant abnormal) will also be summarized. Listings will be provided for all electrocardiograms results collected in this OLE study.

4.9.6 Other Safety Measures

4.9.6.1 Overdose

The incidence of TEAEs associated with overdose will be summarized by MedDRA SOC and PT, if applicable.

4.9.6.2 Physical Examination and Weight

The observed values and the changes from baseline in the weight and body mass index (BMI) will be summarized using the OLE safety analysis set based on OLE data.

4.9.6.3 Local injection tolerability

The incidence of TEAEs associated with local injection tolerability will be summarized by MedDRA SOC and PT, if applicable.

4.10 Pharmacokinetic (PK) Analyses

The PK analysis will be based on the PK analysis set. Descriptive statistics of the serum daxdilimab concentration will be tabulated by visit.

Additional PK analyses may be conducted as appropriate and reported separately from the clinical study report.

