4.3 Rationale for Dose

A 200 mg daxdilimab dose administered Q12W has been selected to evaluate whether this decreased frequency of daxdilimab dosing can maintain clinical efficacy and to reduce the risk of safety and tolerability findings in the long term.

Treatment with daxdilimab in a single-blind, Phase 1b MAD study, resulted in a favorable safety profile and rapid and durable depletion of blood pDCs in all subjects receiving a 150 mg Q4W dose. Depletion of blood pDCs remained decreased until 3 months after the final dose when 90% of subjects recovered to within at least 50% of baseline. The 200 mg Q12W dosing strategy will allow for the evaluation of whether blood pDC depletion and recovery reaches a steady state and can be maintained by less frequent dosing.

A treatment period of 48 weeks is considered sufficient to evaluate long-term safety of daxdilimab and the secondary PK/PD outcome measures selected for this OLE study, and current nonclinical ([Section 2.2.4](#)) safety data supports this treatment duration.

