2.2 Trial Design

This is an open-label study designed to evaluate the long-term safety and tolerability of daxdilimab in participants completing the treatment period of the VIB7734.P2.S1 (RECAST SLE) clinical study. Once a participant has completed the treatment period (through Week 48) of the RECAST SLE study, signed the informed consent form, and met all study

eligibility criteria, he/she may be enrolled in this open label extension (OLE) study. Irrespective of their assigned treatment in the RECAST SLE study, all participants participating in the SLE OLE will be treated with daxdilimab 200 mg SC Q12W in addition to their standard-of-care SLE therapy for 48 weeks. After the treatment period (Week 0 to Week 48), the participants will enter an 8-week safety follow-up (SFU) period (Week 48 to Week 56). The basic study flow diagram is presented in Figure 1. Refer to Protocol for detailed trial design.

[figure not shown]

Figure 1 Study Flow Diagram

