2.3 Sample Size Determination

Sample size determination is based on the number of participants who have completed the treatment period of Study VIB7734.P2.S1 (RECAST SLE). A total of 195 participants have been randomized in the RECAST SLE study. Assuming that 20% of participants will prematurely discontinue treatment, there will be a total of approximately 156 participants who will be eligible for this long-term safety study.

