4.4.4 Pharmacokinetic Analysis Set

The PK analysis set is defined as participants who received any dose of daxdilimab in this OLE study and have at least one measurable PK concentration post dose. The PK analyses will be based on PK analysis set.

4.5 **Participant Disposition**

A summary of participant disposition will be presented for the full analysis set using the categories presented below.

- Completed Week 48 in RECAST SLE
- Enrolled in OLE
- Enrolled but not treated
- Enrolled and treated
- Completed treatment
- Discontinued treatment with reasons
- Completed trial
- Discontinued trial with reasons

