4.8 Exploratory Efficacy Analyses

4.9 Safety Analyses

4.9.1 Adverse Events

Adverse events (AEs) collected in this OLE study will be summarized separately using the OLE safety analysis set and together with the AEs collected in study RECAST SLE using the any daxdilimab analysis set overall and by treatment group. Table 4 presents the definition of treatment-emergent adverse event (TEAE) for reporting purposes.

Study	Definition
OLE	A TEAE is defined as any AE with an onset date on or after the first dose date in the OLE study.

Study	Definition
OLE + RECAST SLE (Any daxdilimab exposure)	A TEAE is defined as any AE with an onset date on or after the first daxdilimab dose date (either in OLE or RECAST SLE study)

Table 4Definition of TEAEs

AEs will be coded using the most recent version of MedDRA. All TEAEs will be summarized overall and by MedDRA system organ class (SOC) and preferred term (PT), by severity and by relationship to daxdilimab. Specific AEs will be counted once for each participant for calculating rates, but all events will be presented in participant listings. In addition, if the same AE occurs multiple times within a particular participant, the highest severity and level of causality will be reported.

In addition, since the duration of exposure to daxdilimab is shorter for the participants who received placebo in the RECAST SLE study, the PYE adjusted incidence rate for the number of participants who experienced TEAE will be included in the combined summary of OLE + RECAST SLE using any daxdilimab analysis set. Refer to Section 4.6 for definition of PYE.

An overall summary table will be showing the number and percentage of participants with at least one event in any of the following categories:

- TEAE
- Treatment-emergent serious adverse event (TESAE)
- TEAE resulting in death
- Grade 3 or higher TEAE using CTCAE v5.0
- TEAE leading to discontinuation of daxdilimab
- Serious and/or grade 3 or higher TEAE
- Daxdilimab related TEAE
- Daxdilimab related TESAE

The following AE summaries will also be provided by SOC and PT:

- TEAEs
- TEAEs resulting in death
- Grade 3 or higher TEAEs using CTCAE v5.0
- TEAE leading to discontinuation of daxdilimab
- Daxdilimab related TEAE
- TESAEs
- Daxdilimab related TESAE

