4.11 Pharmacodynamics

The observed count along with the change and percent change from baseline in pDCs will be summarized descriptively using the OLE safety analysis set based on OLE data.

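### The SAP specifies no breakdown of PK or pDC results by RECAST arm, so Day 1, possibly Week 12, and the early pDC course mix drug-naive and continuing participants

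*SAP*

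**What the plan says.** Everyone in the extension gets one regimen, whatever they had before (SAP 2.2): "Irrespective of their assigned treatment in the RECAST SLE study, all participants participating in the SLE OLE will be treated with daxdilimab 200 mg".

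- **PK (SAP 4.10):** "Descriptive statistics of the serum daxdilimab concentration will be tabulated by visit". The PK analysis set (SAP 4.4.4) is "participants who received any dose of daxdilimab in this OLE study and have at least one measurable PK concentration post dose", which takes in both prior groups.
- **pDCs (SAP 4.11):** the count, change and percent change "will be summarized descriptively using the OLE safety analysis set based on OLE data". That set also contains both groups.
- **Protocol 9.3.3.1 and 9.3.3.3** add no grouping for either endpoint.

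Elsewhere the SAP does separate the groups. SAP 4.9.1 combines extension and RECAST adverse events "using the any daxdilimab analysis set overall and by treatment group", and adds an exposure-adjusted rate because ex-placebo participants have had daxdilimab for less time. SAP 4.4.2 analyses exploratory efficacy by randomised RECAST arm.

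Protocol 4.3 gives the purpose of the 12-weekly regimen: "to evaluate whether this decreased frequency of daxdilimab dosing can maintain clinical efficacy". It then asks whether pDC depletion and recovery settle to a steady state and can be sustained with less frequent dosing.

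**The concern.** PK and pDCs are the secondary endpoints on which prior exposure acts most directly. Under Protocol 8.1, assessments on dosing days are done before the dose. On Day 1 an ex-placebo participant therefore has no drug and no drug-induced depletion, while a continuing participant may have both.

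After Day 1 the groups can move in opposite directions. Ex-placebo participants show onset of depletion. Continuing participants, if they were dosed more often in RECAST, may show partial recovery. Whether depletion is maintained under less frequent dosing can be judged only in people who were already depleted. A single average over both groups can conceal a loss of depletion at the change of regimen.

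**Working it through.** **1. The plan's own figure.** SAP 2.3 states: "A total of 195 participants have been randomized in the RECAST SLE study", and "Assuming that 20% of participants will prematurely discontinue treatment". 195 × (1 − 0.20) = 156, which reproduces the stated number eligible.

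**2. Group sizes.** The placebo share p is not in the documents; assume 1/3 to 1/2, with equal completion across arms.

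- Ex-placebo: 156 × 1/3 = 52, up to 156 × 1/2 = 78.
- Continuing: 104 down to 78.

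**3. Day 1 concentration.** Set the continuing participants' mean to 1 and assume an SD of 0.5. Count ex-placebo values as 0. The SAP sections on PK and missing data give no rule for values below quantitation, so this is an assumption too.

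- Pooled mean = 1 − p
- Pooled SD = √[(1 − p) × 1.25 − (1 − p)²]

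| p | Mean | SD | CV |
|---|---|---|---|
| 1/3 | 0.67 | 0.62 | 94% |
| 1/2 | 0.50 | 0.61 | 122% |

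The pooled mean is 50% to 67% of the continuing mean, and an assumed CV of 50% becomes 94% to 122%.

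**4. How long PK mixing lasts.** Protocol 5.1 equates 3 months with about 5 half-lives: 84/5 = 16.8 days, or 91.3/5 = 18.3 days. Use one-compartment superposition of pre-dose troughs, in units of one 200 mg dose. Let q be the fraction left after 84 days (0.031 or 0.041), and T the continuing participants' trough on Day 1. T assumes steady state and a last RECAST dose one dosing interval earlier.

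- Week 12 ratio, continuing to naive: (T + 1)q / q = 1 + T
- Week 24 ratio: 1 + Tq/(1 + q)

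The RECAST regimen is not in these documents, so three are tried. Each range covers the two half-lives.

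| Assumed RECAST regimen | T | Week 12 ratio | Week 24 ratio |
|---|---|---|---|
| 200 mg every 4 weeks | 0.46–0.53 | 1.46–1.53 | 1.014–1.021 |
| 150 mg every 4 weeks | 0.35–0.40 | 1.34–1.40 | 1.011–1.016 |
| 200 mg every 12 weeks | 0.03–0.04 | 1.03–1.04 | 1.001–1.002 |

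At Weeks 36, 48 and 56 the ratio is at most 1.001. With a ratio R at Week 12, the pooled mean as a share of the continuing mean is [p + (1 − p)R]/R. For p = 1/2 and R = 1.53 this is 83%; for p = 1/3 and R = 1.34 it is 91%. With 12-weekly dosing in RECAST, Week 12 is hardly affected.

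**5. pDCs on Day 1.** Baseline is the value before the first RECAST dose (SAP 4.1.1). Assume ex-placebo change is 0 on Day 1 and continuing participants are depleted by d. The pooled change is −(1 − p)d.

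| d (assumed) | p = 1/3 | p = 1/2 |
|---|---|---|
| 50% | −33% | −25% |
| 80% | −53% | −40% |
| 95% | −63% | −48% |

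**6. Can a pooled curve hide a loss?** Take d = 80% and suppose both groups are at −50% at Week 12. The −50% is only loosely guided by Protocol 4.3, where 90% of Phase 1b subjects had recovered to within at least 50% of baseline 3 months after the last dose. The pooled change then goes from −53% to −50% (p = 1/3), apparently flat, or from −40% to −50% (p = 1/2), apparently deepening. In both cases continuing participants have lost 80 − 50 = 30 points of depletion.

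In general, if both groups reach the same Week 12 value, the pooled mean does not move when that value is −(1 − p)d. The hidden loss is then p × d: from 1/3 × 50 = 17 points to 1/2 × 95 = 48 points.

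**The case against.** The strongest reply is that pooling is inferred from silence. SAP 4.1 sends further presentation details to a Statistical Programming Plan that is not among the documents, Protocol 9.3.1 sorts listings by treatment group, and SAP 4.10 allows additional PK analyses. That stands as a limit on wording: the documents leave the grouping unstated and do not say that the groups will be pooled. It does not close the gap, because the SAP states the grouping in its own text for adverse events and efficacy. The optional PK analyses are not a commitment and do not cover pDCs.

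A reader might also infer that neither secondary summary can be interpreted at all. The documents do not support this. All participants receive the same extension regimen. Of the six PK visits (Day 1 and Weeks 12, 24, 36, 48 and 56), four are essentially unaffected on the implied half-life. The pDC baseline is drug-free in both groups, so once the groups have converged, a loss of depletion would show in a pooled percent change. The SAP also reports medians, quartiles and ranges, which would make a block of zero concentrations visible on Day 1.

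It is fair too that ex-placebo participants can inform the steady-state half of the question in Protocol 4.3, and that the efficacy half is already analysed by arm. What remains is the maintenance of pDC depletion across the change of regimen, which only continuing participants can show.

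**Conclusion.** The point holds as a specification gap with a limited but real effect. Neither SAP 4.10 nor SAP 4.11 carries the split by prior arm that the SAP uses elsewhere. Followed as written, the Day 1 PK summary describes neither group, with a pooled mean 50% to 67% of the continuing mean. Week 12 PK may be affected, depending on the RECAST regimen. PK mixing is negligible from Week 24, where the ratio is at most 1.021.

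For pDCs, the early course can mislead: in the worked example a 30-point loss of depletion appears as a flat or deepening curve. pDC recovery may lag drug clearance, so carry-over after Week 12 cannot be excluded, and the documents do not allow it to be quantified.

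These sizes rest on assumptions for the placebo share, the RECAST regimen, the 50% CV, the depth of depletion, the common Week 12 value and the handling of unquantifiable samples. The half-life comes from the protocol's approximate statement. The summaries are descriptive and no hypothesis is tested, so no error rate or sample size is at stake; the primary safety endpoint is untouched.

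**What to change.** In SAP 4.10 and 4.11, state that serum concentration and pDCs (observed, change and percent change) are summarised by visit, by randomised RECAST arm and overall, with Day 1 shown by arm only. Add that maintenance of depletion under less frequent dosing will be judged in the ex-daxdilimab participants.

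The cost is two sentences of SAP text and extra table columns. The data are already collected and the randomised arm is already used in other analyses. On the assumptions above, about 52 to 78 ex-placebo and 78 to 104 continuing participants are enough for descriptive tables.

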4.11 Pharmacodynamics

The observed count along with the change and percent change from baseline in pDCs will be summarized descriptively using the OLE safety analysis set based on OLE data.

4.12 Immunogenicity

The ADA status will be summarized using the any daxdilimab analysis set by the categories defined in Table 5. The ADA incidence rate may also be summarized, where the incidence is the proportion of the participants with ADA positive post-baseline only or boosted their preexisting ADA during the study period. The cutoff for the boosted ADA will be determined before the database lock. If data allow, the ADA titer for the ADA positive participants will be summarized, and the impact of ADA on PK, efficacy and safety will be evaluated.

Table 5Definition of ADA Status

ADA Status	Definition
Prevalence (Positive during the study)	ADA positive observed at least once during the study (baseline included)
Negative during the study	ADA positive not observed at any visit during the study (baseline included)
Baseline positive	ADA positive observed at baseline regardless the post-baseline ADA status

ADA Status	Definition
Post-baseline positive	ADA positive observed at least once during post-baseline regardless the baseline ADA status
Only baseline positive	ADA positive observed at baseline but not observed at any time post-baseline
Only post-baseline positive (treatment- induced)	ADA positive not observed at baseline but observed at least once post-baseline
Both baseline and post-baseline positive	ADA positive observed at baseline and observed at least once post-baseline
Persistent positive	Treatment-induced ADA positive at ≥ 2 post-baseline assessments (with ≥ 16 weeks between first and last positive) or positive at last post-baseline assessment
Transient positive	Treatment-induced ADA post-baseline positive but does not fulfil the criteria of persistent positive

Table 5Definition of ADA Status

ADA = anti-drug antibodies.

5 SOFTWARE

SAS® Software Version 9.4. SAS Institute Inc., Cary, NC, USA.

APPENDIX 1 PREDNISONE EQUIVALENT OF ORAL GLUCOCORTICOID DOSE

Oral GCs other than prednisone may be used PO at the equivalent doses shown in **Error! Reference source not found.**

